1.0 TRIAL SUMMARY

Name of Sponsor: Takeda Development Center Americas, Inc.	Compound: TAK-954
Study Number: TAK-954-1004	Phase: 1
Protocol Title: A Fixed Sequence, Open-Label, 2-Period Crossover Trial to Evaluate the Effect of the Potent Cytochrome P-450 3A4 Inhibitor Itraconazole on the Pharmacokinetics of TAK-954 in Healthy Adult Subjects	
Trial Design: 
This is a phase 1, single-sequence, open-label, 2-period crossover trial in approximately 10 healthy male and female (non-childbearing potential) subjects aged 18 and 55 years (inclusive). The trial is designed to investigate the effect of a potent cytochrome P-450 (CYP) 3A4 inhibitor (itraconazole) on the pharmacokinetics (PK) of TAK-954. TAK-954 will be administered as a single 60-minute intravenous (IV) infusion.
 
The trial will include a Screening Visit, Trial Period 1 (6 days), a washout (a minimum of 7 days between doses in Period 1 Day 1 and Period 2 Day 1), Trial Period 2 (9 days), and a Follow-up Visit. Eligible subjects will be allocated to the trial treatment by non-random assignment on Day 1 of Trial Period 1 and will receive a 0.2 mg single dose TAK-954 IV on this day and on Day 4 of Trial Period 2 at approximately the same time (between 0600 and 0900). In Trial Period 2, subjects will receive 200 mg once daily (QD) itraconazole orally on Days 1 to 8 at approximately the same time (between 0600 and 0900) and a single dose of 0.2 mg TAK-954 on Day 4. Itraconazole will be administered as 2 x 100 mg capsules. After completion of the trial (or after subject withdrawal), all subjects will return for a Follow-up Visit 10 to 14 days after their last dose of trial drug.
	
Primary Objective: 
• To evaluate the effect of the potent CYP3A4 inhibitor itraconazole on the single-dose PK of TAK-954.	
Secondary Objectives: 
• To evaluate the safety of a single IV dose of TAK-954 in the presence and absence of a potent CYP3A4 inhibitor.	
Subject Population: Healthy male and female (non-childbearing potential) subjects.	
Number of Subjects: Approximately 10 subjects will complete this trial.	Number of Sites: 1 site
Dose Levels: 
• TAK-954 0.2 mg• Itraconazole 200 mg QD	Route of Administration: 
• TAK-954 IV• Itraconazole oral
Duration of Treatment: Two doses of TAK-954. Eight doses of itraconazole.	Period of Evaluation: Approximately 7 to 8 weeks
Main Criteria for Inclusion: Healthy male and female (non-childbearing potential) subjects who are aged 18 to 55 years, inclusive, with a body mass index (BMI) between 18 to 30 kg/m ² , and a body weight >50 kg.	
Main Criteria for Exclusion: Subjects who have a history of clinically significant endocrine, gastrointestinal (GI [including motility disorder and intestinal obstruction]), cardiovascular, hematological, hepatic, immunological, renal, respiratory, genitourinary, or major neurological (including stroke and chronic seizures) abnormalities or diseases will be excluded from the trial.	

Endpoints and Criteria for Evaluation:

Primary endpoints:

Plasma PK parameters (maximum observed concentration [C_{max}] and area under the concentration-time curve from time 0 to infinity, calculated using the observed value of the last quantifiable concentration [AUC_{∞}]) for TAK-954 will be analyzed on Day 1 of Trial Period 1 and on Day 4 of Trial Period 2.

Safety endpoints:

Safety and tolerability will be assessed through physical examinations, electrocardiograms (ECGs), vital signs, and laboratory assessments as well as collection of spontaneous adverse events.

Statistical Considerations:

Pharmacokinetics:

The PK parameters of TAK-954 (and metabolites, if possible) will be summarized by regimen using descriptive statistics. Linear and semilogarithmic plots of the mean and individual concentration-time curves will be provided. Individual plasma concentration and PK parameter data will be presented in the data listing.

For evaluation of potential effect of itraconazole on TAK-954 PK, paired t-tests and associated confidence intervals will be determined on the natural logarithms of C_{max} and AUCs to assess the exposure between regimens (TAK-954 alone and TAK-954 with itraconazole). The geometric mean of the relative bioavailability of the TAK-954 with itraconazole regimen relative to the TAK-954 alone regimen and the associated 90% confidence intervals will be determined by exponentiating the appropriate estimates for the difference between regimens in the log-transformed parameters.

Safety:

[figure not shown]
Safety data will be presented by regimen. Treatment-emergent adverse events (TEAEs) will be summarized by causal relationship to the trial drug and by intensity. Clinical laboratory variables, ECGs, and vital signs parameters (uncorrected and corrected QT intervals, PR, and QRS and heart rate) will be summarized with descriptive statistics for period baseline, postdose, and change from period baseline to postdose values.

Sample Size Justification:

Approximately 10 subjects will complete this trial. With this sample size, a 2-sided 95.0% CI for the geometric mean ratio of C_{max} for TAK-954 when administered with and without itraconazole will have 90% probability of excluding 1.25 (the upper bound of the bioequivalence range) if itraconazole increases the C_{max} for TAK-954 by at least 50%. This calculation assumes that the CI is based on the t statistic, that the distance from the mean to the lower bound of the CI on the natural-log scale is 0.182, and that the true SD of differences on the natural-log scale is 0.187 as estimated from C_{max} values reported for Cohort 1 in Theravance Protocol No. 0095. Assuming the intrasubject variation observed for area under the concentration-time from 0 to t in that cohort (SD=0.129), a 2-sided 95.0% CI for the geometric mean ratio of AUC_{∞} for TAK-954 when administered with and without itraconazole will have greater than 99% probability of excluding 1.25 if itraconazole increases AUC_{∞} for TAK-954 by at least 50%.

Subjects who drop out may be replaced at the discretion of the investigator in consultation with the sponsor.

2.0 TRIAL SCHEMATIC

PK=pharmacokinetic.

3.0 SCHEDULE OF TRIAL PROCEDURES

Assessment	Screening	Trial Period 1 (a)						Trial Period 2							Follow-up/Early Termination		
		Day	-28 to -2	-1	1	2	3	4 to 6	-1	1	2 to 3	4	5	6	7	8	9
Administrative Procedures																	10-14 days after last dose of trial drug
Informed consent	X																
Inclusion/exclusion criteria	X	X															
Medical history/demographics	X																
Prior and concomitant medication review			-----Continuous review-----														
Clinic Procedures/Assessments																	
Full physical examination	X	X															X
Semirecumbent vital signs (heart rate [HR], systolic blood pressure [SBP] and diastolic blood pressure [DBP])	X		X(b)	X	X			X	X	X	X	X	X			X	X
Vital signs (respiratory rate, oral [at the floor of the mouth]/tympanic temperature) rate	X		X(b)					X									
Height	X																
Weight	X																
Body mass index (BMI)	X																
Standard 12-lead electrocardiogram (ECG)	X		X(b)		X		X				X				X		X
CCI																	
Adverse event (AE) monitoring			-----Continuous review-----														
Laboratory Procedures/Assessments																	
Serum chemistry	X	X			X		X							X			X
Hematology	X	X			X		X							X			X
Urinalysis	X	X			X		X						X			X	
Serum follicle-stimulating	X																

CONFIDENTIAL

Assessment	Screening	Trial Period 1 (a)						Trial Period 2						Follow-up/Early Termination		
		-28 to -2	-1	1	2	3	4 to 6	-1	1	2 to 3	4	5	6	7	8	9
Day	-28 to -2	-1	1	2	3	4 to 6	-1	1	2 to 3	4	5	6	7	8	9	10-14 days after last dose of trial drug
hormone (FSH)																
Urine drug screen	X	X					X									
Urine alcohol test/alcohol breath test (d)	X	X					X									
HIV test	X															
Hepatitis panel	X															
Pharmacokinetics (PK) Evaluations																
Plasma samples for TAK-954 (e)			X	X	X	X				X	X	X	X	X	X	
Urine sample for TAK-954 PK (f)			X	X	X					X	X	X				
Pharmacogenomic (PGx) Evaluations																
Blood sample for DNA PGx			X													
Blood sample for RNA PGx			X													
Drug Administration																
TAK-954 dosing			X								X					
Itraconazole dosing								X	X	X	X	X	X	X		
Other																
Confinement		X	X	X	X			X	X	X	X	X	X	X		
Meals		X	X	X	X			X	X	X	X	X	X	X		

(a) A minimum of 7 days between doses in Period 1 Day 1 and Period 2 Day 1.

(b) Assessments at predose (within 30 minutes), 1, 2, 4, 8, and 12 hours postdose (relative to TAK-954 start of infusion).

(c) CCI

(d) An alcohol breath test may be performed at the discretion of the investigator.

(e) Time points for PK blood samples for TAK-954: predose (within 30 minutes), and 0.33, 0.5, 0.67, 1 (just after the end of infusion), 1.5, 2, 3, 4, 6, 12, 24, 36, 48, 72, 96, and 120 hours postdose (relative to TAK-954 start of infusion).

(f) Urine collected at predose, 0 to 6, 6 to 12, 12 to 24, and 24 to 48 hours relative to TAK-954 infusion start in Trial Periods 1 and 2.

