5.1.2 Secondary Objective

The secondary objectives of the trial are to evaluate the safety of single-dose IV doses of TAK-954 in the presence and absence of a potent CYP3A4 inhibitor.

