9.4 Trial Drug Administration

Eligible subjects will be allocated to trial treatment by non-random assignment on Day 1 of Trial Period 1 and will receive a 0.2 mg single-dose TAK-954 IV on this day and on Day 4 of Trial Period 2 at approximately the same time (between 0600 and 0900). In Trial Period 2, subjects will receive 200 mg QD itraconazole orally on Days 1 to 8 at approximately the same time (between 0600 and 0900). Itraconazole will be administered as 2 x 100 mg capsules and witnessed by the investigator and/or trial staff. The bioavailability of itraconazole when administered as capsules is increased under fed compared with fasted conditions and therefore, itraconazole will be administered after a standard (moderate-fat) breakfast (consumed within 30 minutes before dosing). The TAK-954 infusion will start 1 hour after itraconazole administration on Day 4 of Trial Period 2. To maintain similar conditions in each trial period, subjects will also receive a standard (moderate-fat) breakfast 1.5 hours before TAK-954 IV administration in Trial Period 1.

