11.1.4 Safety Analysis

The safety set will be used for all summaries of safety parameters. These summaries will be presented by TAK-954 alone, itraconazole alone, and TAK-954 with itraconazole.

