11.1.4.3 Vital Signs

Baseline, postdose, and changes from Baseline in vital sign measurements will be summarized. All vital sign data will be provided in the data listings.

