7.11.3 Vital Signs

Vital sign measurements include body temperature, pulse, respiratory rate, and blood pressure. Refer to [Appendix A](#) for scheduled vital signs measurement visits.

Individual results for vital sign measurements that meet the Takeda predefined vital signs MAV criteria in [Appendix C](#) will be presented in a data listing. If a subject has a MAV for a particular vital sign parameter, all visits for that subject for that parameter will be listed.

All vital sign data will be presented in the listings. Vital sign MAVs will be flagged in the listings.

7.11.4 12-Lead ECGs

The scheduled 12-lead ECG data will be collected according to [Appendix A](#). The ECG parameters include heart rate, PR interval, QRS interval, QT interval, and QTc interval (Fredericia's correction).

Individual results for 12-lead ECG measurements that meet the Takeda predefined 12-lead ECG MAV criteria in [Appendix D](#) will be presented in a data listing. If a subject has a MAV for a particular ECG parameter, all visits for that subject for that parameter will be listed.

All ECG data will be presented in the listings. ECG MAVs will be flagged in the listings.

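### Respiratory rate and temperature have no scheduled reading after TAK-954 in the itraconazole period, against five per subject after TAK-954 alone, although vital signs are to be presented by regimen.

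*Protocol*

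**What the plan says.** **Schedule.** Protocol Section 3.0 has two vital-sign rows. One is "Semirecumbent vital signs (heart rate [HR], systolic blood pressure [SBP] and diastolic blood pressure [DBP"; the other is "Vital signs (respiratory rate, oral [at the floor of the mouth]/tympanic temperature) rate". The second row has three marks: Screening, Period 1 Day 1 with footnote (b), and one plain mark early in Period 2. SAP Appendix A repeats these three marks. Footnote (b) reads "Assessments at predose (within 30 minutes), 1, 2, 4, 8, and 12 hours postdose (relative to TAK-954 start of infusion".

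**Dosing.** Protocol Section 9.4 says that subjects "will receive a 0.2 mg single-dose TAK-954 IV on this day and on Day 4 of Trial Period 2". Day 4 is therefore the only day on which TAK-954 is given with itraconazole.

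**Objective and analysis.** The secondary objective (protocol Section 5.1.2) is to "evaluate the safety of single-dose IV doses of TAK-954 in the presence and absence of a potent CYP3A4 inhibitor". On safety summaries, protocol Section 11.1.4 says: "These summaries will be presented by TAK-954 alone, itraconazole alone, and TAK-954 with itraconazole". Section 11.1.4.3 adds: "Baseline, postdose, and changes from Baseline in vital sign measurements will be summarized". Neither section makes an exception for respiratory rate or temperature.

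**SAP.** Section 7.11.3 says: "Vital sign measurements include body temperature, pulse, respiratory rate, and blood pressure". It refers to Appendix A for timing and plans listings with markedly abnormal values (MAVs) flagged. Appendix C sets MAV limits for temperature (below 35.6 or above 37.7 °C) and none for respiratory rate.

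**Narrative text.** Protocol Section 9.1.7 describes how temperature is measured but gives no time points for either measure. Section 9.0 allows unscheduled procedures at the investigator's discretion.

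**The concern.** The safety question compares TAK-954 with and without the inhibitor. For these two measures the schedule observes only one side of that comparison after dosing. The analysis text treats them like any other vital sign: the protocol promises baseline, postdose and change values, and the SAP promises listings with MAV flags. The schedule cannot supply the combination's share of either.

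At stake is a small part of the secondary objective. The combination regimen would contribute no scheduled postdose respiratory rate or temperature to the protocol's summaries or to the SAP's listings. The temperature MAV screen would test five timed postdose readings per subject in Period 1 and none after the Day 4 dose. Finding no temperature MAV with the combination would then say nothing about the combination.

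**Working it through.** No power or alpha figure bears on this point, so the check is a reading of the two schedule tables followed by a count.

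**1. Where the marks fall.** The header gives 16 columns: Screening, five in Period 1, nine in Period 2 (Day -1, 1, 2 to 3, 4, 5, 6, 7, 8, 9) and Follow-up. In the tables as read from the PDF, the clinical-assessment rows have 17 cells, so some marks may sit one cell to the right of their true column.

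| Row | Protocol 3.0, marked cells | SAP Appendix A, marked cells |
|---|---|---|
| Respiratory rate, temperature | 1, 3(b), 8 | 1, 3(b), 8 |
| HR, SBP, DBP | 1, 3(b), 4, 5, 8 to 13, 16, 17 | 1, 3(b), 4, 5, 8 to 10, 11(b), 12, 13, 16, 17 |
| ECG | 1, 3(b), 5, 7, 11, 15, 17 | 1, 3(b), 5, 8, 11(b), 16, 17 |
| TAK-954 dosing | 3, 11 | 3, 10 |

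**2. Could the single Period 2 mark be Day 4?**
- By the printed header, cell 8 is Day 1 and Day 4 is cell 10.
- If the row is shifted by one, cell 8 is Day -1 and Day 4 is cell 11. Cell 11 is where the SAP puts footnote (b) for the HR/BP and ECG rows.
- The mark is therefore 2 or 3 cells before Day 4. A one-cell shift cannot close that gap.
- Even if the mark did belong on Day 4, it carries no footnote (b). In the SAP table, where HR/BP and ECG do carry it on Day 4, this row would still lack the timed set.

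**3. Does any text add a reading?** Protocol Sections 9.0 and 9.1.7 and SAP Section 7.11.3 give no further time point. The SAP points back to the same table. Nothing is marked at Follow-up.

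**4. Count per subject, for each measure.**
- Footnote (b) has 1 predose and 5 postdose times, so 1 + 5 = 6.
- TAK-954 alone (Period 1 Day 1): 1 same-day predose, 5 postdose.
- TAK-954 with itraconazole (Period 2 Day 4 onward): 0 same-day predose, 0 postdose.
- Over 10 subjects, postdose: 5 × 10 = 50 against 0 × 10 = 0.

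**5. What the one Period 2 reading can do.** It falls 3 days before the TAK-954 dose if taken on Day 1, or 4 days before if taken on Day -1. It might serve as a period baseline. With no later scheduled value, no change from baseline can be formed for the combination.

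**The case against.** The strongest reply is that this is deliberate, proportionate monitoring:
- Protocol Section 6.2.1 reports no respiratory-rate signal after multiple oral dosing. The effects it describes that could call for monitoring are cardiovascular, and HR, blood pressure and ECG are scheduled on Period 2 Day 4.
- Subjects are confined that day, adverse events are reviewed continuously, and unscheduled readings are allowed.
- Section 9.1.7 names only heart rate and the two blood pressures in its list of vital signs, and Appendix C has no respiratory-rate limit.
- Section 11.1.4.3 does not itself say by regimen.

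Much of this stands and limits the point. It does not remove the conflict. The by-regimen presentation comes from Section 11.1.4, which covers all safety summaries. SAP Section 7.11.3 expressly includes both measures. If lighter Period 2 monitoring was intended, no section says so.

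A reader might infer several stronger things that the documents do not support:
- **Empty cells in the SAP's summary tables.** The SAP plans only listings and MAV flags for vital signs, so it has no such cells. The postdose and change summaries are promised in the protocol.
- **No readings in the regimen with the higher exposure.** Section 6.2.1 says only that increases may be observed. They are not established.
- **The secondary safety objective cannot be met.** Adverse events, laboratory tests, HR, blood pressure and ECG still inform it.
- **A missed respiratory-rate MAV.** No such criterion exists.

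**Conclusion.** The point holds for these two measures only. As scheduled, each has 5 postdose readings per subject after TAK-954 alone and 0 after TAK-954 with itraconazole (50 against 0 over 10 subjects). Scheduled data therefore cannot support a postdose comparison between those regimens. Only an unscheduled reading could show a temperature MAV after the combination.

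The conclusion assumes that the tables were read from the PDF without losing a mark. The same three marks in both documents support that, but the original tables should be checked. Whether the Period 2 mark is Day -1 or Day 1 does not matter, because both precede Day 4.

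The consequence is modest: the primary PK endpoints and the Day 4 HR, blood pressure and ECG assessments are untouched. It is worth correcting because the schedule and the analysis text disagree and the remedy is very cheap.

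**What to change.** Reconcile the schedule with the analysis text in both documents.

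**Preferred.** In protocol Section 3.0 and SAP Appendix A, add respiratory rate and temperature to the HR/BP readings on Period 2 Day 4, with footnote (b), so that the two TAK-954 dosing days match. The protocol's HR/BP mark on Day 4 has no footnote (b), while the SAP's does. That difference should be settled in the same edit so that the times are defined in both tables. The cost is one mark per table and 6 readings of each measure per subject (6 × 10 = 60 per measure over 10 subjects), taken while subjects are confined and already having HR/BP measured.

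**If the omission is intended.** State in protocol Section 11.1.4.3 and SAP Section 7.11.3 that respiratory rate and temperature are not compared between regimens. This costs a sentence in each document and gives up the comparison openly.

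In either case, confirm from the original table whether the existing Period 2 mark is Day -1 or Day 1.

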11.1.4.4 ECGs

Baseline, postdose, and changes from Baseline in quantitative ECG parameters will be summarized by regimen. Shift tables for each will be generated to show the investigator's ECG interpretations at each postdose collection by the interpretation at Baseline.

All ECG data will be provided in the data listings.

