8.0 REFERENCES

Appendix A Schedule of Study Procedures

Assessment	Screening	Trial Period 1 (a)						Trial Period 2							Follow-up/Early Termination		
		Day	-28 to -2	-1	1	2	3	4 to 6	-1	1	2 to 3	4	5	6	7	8	9
Administrative Procedures																	10-14 days after last dose of trial drug
Informed consent	X																
Inclusion/exclusion criteria	X		X														
Medical history/demographics	X																
Prior and concomitant medication review																	
Clinic Procedures/Assessments																	
Full physical examination	X	X															X
Semirecumbent vital signs (heart rate [HR], systolic blood pressure [SBP] and diastolic blood pressure [DBP])	X		X(b)	X	X			X	X	X	X(b)	X	X			X	X
Vital signs (respiratory rate, oral [at the floor of the mouth]/tympanic temperature) rate	X		X(b)					X									
Height	X																
Weight	X																
Body mass index (BMI)	X																
Standard 12-lead electrocardiogram (ECG)	X		X(b)		X			X			X(b)					X	X
Bowel movement assessment (c)			X	X	X			X	X	X							
Adverse event (AE) monitoring																	
Laboratory Procedures/Assessments																	
Serum chemistry	X	X			X		X							X			X
Hematology	X	X			X		X							X			X
Urinalysis	X	X			X		X							X			X
Serum follicle-stimulating	X																

CONFIDENTIAL

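### Protocol 3.0, as extracted, times ECGs and semirecumbent vital signs after the Period 1 infusion only, while SAP Appendix A times them after both infusions

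*Protocol*

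**What the plan says.** **Schedule.** Footnote (b) has the same wording in Protocol 3.0 and SAP Appendix A: "Assessments at predose (within 30 minutes), 1, 2, 4, 8, and 12 hours postdose (relative to TAK-954 start of infusion". It applies only to cells that carry the mark. Two rows matter here, labelled alike in both documents: "Standard 12-lead electrocardiogram (ECG" and "Semirecumbent vital signs (heart rate [HR], systolic blood pressure [SBP] and diastolic blood pressure [DBP". In the Protocol each of these rows has one X(b), on Period 1 Day 1, and a plain X on Period 2 Day 4. In the SAP each has X(b) on both days.

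**Analysis.** Protocol 1.0 says that laboratory, ECG and vital-sign data will be "summarized with descriptive statistics for period baseline, postdose, and change from period baseline to postdose values". Section 11.1.4.4 says that "changes from Baseline in quantitative ECG parameters will be summarized by regimen", and plans shift tables of the investigator's "ECG interpretations at each postdose collection by the interpretation at Baseline". Section 11.1.4.3 says "Baseline, postdose, and changes from Baseline in vital sign measurements will be summarized". Section 11.1.4 splits the safety summaries by TAK-954 alone, itraconazole alone and the combination.

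**Other Protocol text on timing.** Section 9.1.10 requires a predose ECG for each period and has a QTcF rule that can act at any postdose time point, but it does not list the time points. Section 9.1.7 sets posture up to 4 hours after dosing, not measurement times. Section 6.2.3 only orders ECGs and vital signs ahead of a PK draw when they coincide. Section 6.1 says that safety is monitored throughout each dosing period.

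**The concern.** Period 2 Day 4 is the only infusion given under CYP3A4 inhibition. Section 6.2.1 explains that the 0.2 mg dose was kept below the highest IV dose studied so as to leave room for a rise in exposure. It is therefore the infusion at which timed post-infusion readings matter most.

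In the Protocol's semirecumbent row, a plain X is also the entry for days with no infusion, such as Period 1 Days 2 and 3. A site reading the Protocol table could therefore treat Day 4 as one reading at any time, and nothing in the cell says that it must follow the infusion. The next ECG in the row comes only on Day 8 or Day 9, depending on how the columns are read.

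Two things would be at stake. First, the planned change summaries and shift tables would have postdose ECGs at 1, 2, 4, 8 and 12 hours for TAK-954 alone and no matching series for the combination, so the secondary objective would lack like-for-like data. Second, the QTcF rule in 9.1.10 can act only on ECGs that are taken.

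**Working it through.** The plan gives no figure to reproduce. The check compares table cells and counts readings.

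**1. Which cell is Period 2 Day 4.** The headings give 16 columns, but the ECG and semirecumbent rows have 17 cells after the label. If the extra cell lies between the two periods, Day 4 is cell 11. The SAP supports this: its second (b) sits in cell 11, and (b) is timed from the TAK-954 infusion, which in Period 2 happens only on Day 4.

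**2. The cells side by side** (number = position after the row label).

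| Row | Protocol 3.0 | SAP Appendix A |
|---|---|---|
| Semirecumbent HR/SBP/DBP | 1, 3(b), 4, 5, 8, 9, 10, **11**, 12, 13, 16, 17 | 1, 3(b), 4, 5, 8, 9, 10, **11(b)**, 12, 13, 16, 17 |
| 12-lead ECG | 1, 3(b), 5, 7, **11**, 15, 17 | 1, 3(b), 5, 8, **11(b)**, 16, 17 |

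In the semirecumbent row, 16 of the 17 cells are identical and only the (b) at cell 11 differs. In the ECG row the same (b) differs, and two other marks sit one column apart (7 against 8, 15 against 16).

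**3. Whether other Protocol text fills the gap.** Sections 6.1, 6.2.3, 9.1.7 and 9.1.10 contain no postdose clock times for ECG or vital signs. Footnotes (e) and (f) do give times that apply in Period 2, but for PK blood and urine only. Footnote (f) names both periods; footnote (b) does not.

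**4. Counts.** Footnote (b) is predose plus 1, 2, 4, 8 and 12 h, which is 6 readings, 5 of them postdose. Sample size: 10 subjects (Protocol 11.3).

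| Per measure (ECG, or semirecumbent vital signs) | Protocol 3.0 as extracted | SAP Appendix A |
|---|---|---|
| Timed postdose readings, Period 1 Day 1 | 5 × 10 = 50 | 5 × 10 = 50 |
| Timed postdose readings, Period 2 Day 4 | 0 × 10 = 0 | 5 × 10 = 50 |
| All scheduled readings, Period 2 Day 4 (one per plain X) | 1 × 10 = 10 | 6 × 10 = 60 |

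On Day 4 the two documents differ by 60 − 10 = 50 readings for each measure.

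**The case against.** **The Protocol table is visibly damaged.** Besides the ECG shifts, the Protocol's urinalysis marks sit one column away from chemistry and hematology, whereas in the SAP all three align. The Protocol's Period 2 TAK-954 dosing mark falls at cell 11, although plasma sampling starts at cell 10. A table in this state is a weak basis for a claim about single cells, and a broken table is not a plan error. This stands as a caveat: loss of the two (b) marks in extraction cannot be excluded. But the faults seen are shifts of position, not lost marks. The Period 1 (b) survived in both rows, and the semirecumbent row otherwise matches the SAP cell for cell.

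**The intent is readable.** Footnote (b) is tied to the TAK-954 infusion, which occurs in both periods; 9.1.10 wants a predose ECG in each; the SAP shows X(b) on Day 4. Timed Day 4 readings were probably intended, and that stands. It makes the fix easy but does not make it unnecessary, because sites work from the Protocol.

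**The stakes can be overstated.** A reader might infer that five readings against one would bias the comparison, giving TAK-954 alone the larger maximum change or more flagged subjects. The documents do not support putting a size on that. Neither plans a maximum-change statistic or a count of flagged subjects by regimen, and SAP 7.11.3 and 7.11.4 describe only listings with marked abnormalities flagged. What remains is missing matched data for the Protocol's summaries and shift tables.

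**Conclusion.** The point holds in limited form and should be corrected. As extracted, Protocol 3.0 sets no timed postdose ECG or semirecumbent vital signs on Period 2 Day 4, and SAP Appendix A sets five of each per subject. For 10 subjects that is 0 against 50 timed postdose readings for each measure. This rests on reading cell 11 as Day 4 and on the Protocol PDF truly lacking the two marks. If the marks are there, the discrepancy disappears.

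Four wider readings are not supported:

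- **No Day 4 safety assessment, or deliberately lighter monitoring under inhibition.** The Protocol does schedule an ECG and semirecumbent vital signs that day; only the timed series is missing, and nothing suggests that this was intended.
- **No Period 2 postdose times at all.** PK blood and urine are timed.
- **The same fault in the respiratory rate and temperature row** ("Vital signs (respiratory rate, oral [at the floor of the mouth]/tympanic temperature) rate"). That row is identical in both documents, with (b) on Period 1 Day 1 only. Taking these two measures less often is a minor sampling choice, not a discrepancy.
- **A need for an added AV-conduction trigger in 9.1.10.** Section 6.2.1 reports AV dissociation at 10 mg oral, but investigator interpretation of each ECG, cardiologist review as needed and the withdrawal criteria already give cover.

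**What to change.** First check the original Protocol table. If (b) is absent there, change X to X(b) in the Period 2 Day 4 cells of Protocol 3.0 for 12-lead ECG and semirecumbent vital signs, to match SAP Appendix A. The SAP needs no change.

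The cost is a two-cell Protocol amendment. It adds no assessments beyond the SAP. Against a literal reading of the Protocol it adds 6 − 1 = 5 ECGs and 5 sets of vital signs per subject. Under Section 9.5 subjects stay in the unit until the morning of Day 7. Four of the five postdose times (1, 2, 4 and 12 h) coincide with PK draws already due under footnote (e); only the 8 h reading stands alone.
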